 81 spread across hundreds of genes will dilute timelines for data collection and analysis objectives  
 82 within targeted genes. A solution is to create a universal registry open to all rare RD genes, to  
 83 cross-sectionally characterize patients within all rare RD genes (mild, moderate, and severe  
 84 vision loss) so they are ready to be enrolled into a subsequent universal longitudinal natural

85 history study as their gene is selected. This two-phase platform will (1) eliminate repetitive  
 86 processes like certification, training, regulatory approval, contract agreements, (2) reduce costs  
 87 and accelerate timelines for longitudinal studies and (3) leverage a large sample size and  
 88 standardized data collection in the cross-sectional study to explore the extent to which genes with  
 89 common mechanisms of disease have similar clinical manifestations (e.g., determine if and how  
 90 some genes may be pooled in some analyses).

91 **1.3 Study Objectives**

92 **Registry Objectives**

93 **1. Genotype Characterization**

94 a. Establish a database of patients completing a standardized genetic screening  
 95 process confirming retinal dystrophy is associated with disease-causing genetic  
 96 variants (and thereby confirmed genetically eligible for a potential **natural**  
 97 **history study**)

98 b. Evaluate characteristics of genetic variants

99 **2. Cross-Sectional Phenotype Characterization\***

100 a. Characterize cross-sectional retinal dystrophy associated with disease-causing  
 101 genetic variants using functional and structural measures, within gene

102 i. *Ideally where within-gene sample size is 20 or more*

103 b. Structure-function relationships will also be explored within-gene

104 i. *Ideally where within-gene sample size is 20 or more*

105 c. Risk factors for disease severity will also be explored within-gene

106 i. *Ideally where within-gene sample size is 40 or more*

107 **3. Establish a Link to My Retina Tracker Registry (MRTR)**

108 a. Register MRTR participants for exploratory analysis of data between registry  
 109 databases, as permissible within the scope of signed informed consent(s)

110 **4. Ancillary Exploratory Studies - Pooling of Genes**

111 a. Explore whether phenotype-genotype associations within biological mechanisms  
 112 or other factors (such as age or disease duration) will allow pooling of genes for  
 113 cross-sectional analysis objectives

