#### 1116 9.1.1 General Considerations

1117 Both eyes of a participant will be assessed for the main ocular measures of interest. Thus, if there  
1118 are N participants, 2N eyes will be available for analysis. However, outcome measures from two  
1119 (2) eyes of a person are typically strongly correlated ( $r \geq 0.5$ ). The contribution of information  
1120 from the two (2) eyes in this case is  $(2/(1+r))$  instead of two (2). Values for the multiplier to the  
1121 number of participants to obtain an effective sample size are given below in **Table 9-1**. The  
1122 correlation between eyes (inter-eye correlation) for each outcome measure is not known. We  
1123 assume an inter-eye correlation of 0.8 throughout all sample size calculations throughout section  
1124 1.1. This assumption is conservative in that it requires a higher number of participants than lower  
1125 plausible values of r.

1126 **Table 9-1. Multiplier to Obtain Effective N Based on Inter-Eye Correlation**

r	0.0	0.1	0.2	0.3	0.4	0.5	0.6	0.7	0.8	0.9	1.0
Multiplier for Effective N	2.00	1.82	1.67	1.54	1.43	1.33	1.25	1.18	1.11	1.05	1.00

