1215 ➤ **Figure 9-1** evaluates the **power to detect differences** in percent change from baseline to  
 1216 four (4) years among two (2) subgroups of equally distributed sizes, under various  
 1217 assumptions of true mean difference (x-axis) and standard deviation (SD) of the  
 1218 distribution of percent change. If subgroups are not equally sized, the smallest detectable  
 1219 difference (with the same power) will be larger. All calculations are based on a Type I ( $\alpha$ )  
 1220 error rate of 0.05.

1221 ○ For example, with a total sample size of twenty (20), assuming ten (10) in each of  
 1222 two (2) subgroups, to have power of 80% or more, the true difference needs to be  
 1223 approximately 1.25 SDs (a mean difference of 25% if the SD of the percent  
 1224 change over four (4) years 20%)

1225 ➤ **Also Note:** *Within-subgroup* point estimates and CIs will also be important. **Table 9-3**  
 1226 above can be applied to potential subgroup sample sizes as well to consider the precision  
 1227 that would be observed.

1228

1229

[figure not shown]
1230

1231

[figure not shown]
1232

1233 **Figure 9-1 Power to Detect Differences in Subgroups**

1234

1235

1236 **NHS Sample Size Example**

1237 The following is an example template of using the tables above and a set of assumptions for a  
 1238 given gene of interest to determine the impact on NHS Objectives.

Target Gene	MYO7A
Target Sample Size	50
Data to consider for assumptions	
Data
 
 
• RUSH2A Data – Mean (SD) percent change at 24M 
 
○ Visual Acuity: -2.3 (5.1)%
 
○ OCT EZ area: -2.2 (21.8)%
 
○ Static Perimetry HOV: -12.4 (28.2)%
 
 
 
 
Assume:
 
 
• Inter-eye correlation = 0.8
 
• SD for percent change at 4 years                     
 
○ Visual Acuity → 5%
 
○ OCT EZ area → 20%
 
○ Static Perimetry HOV → 30%
 
 
 

NHS Objective 1 (Natural History)	The half-width of a 95% CI around the point estimate for mean percent change at 4 years would be		
	Visual Acuity	OCT EZ area	Static Perimetry HOV
	1%	5%	8%
NHS Objective 2 (Structure-Function Relationship)	The 95% CI around correlation between any two outcome measures would be		

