	if the observed correlation <math>r = 0.3</math>	(0.02, 0.53)	
	if the observed correlation <math>r = 0.5</math>	(0.26, 0.68)	
	if the observed correlation <math>r = 0.8</math>	(0.67, 0.88)	
NHS Objective 3 (Risk Factors for Progression)	A comparison of two equal-sized subgroups (N=25 each group) would have about 80% power to conclude there is a difference if the true difference is		
	Visual Acuity	OCT EZ area	Static Perimetry HOV
	4%	15%	23%*
	[Type I ( $\alpha$ ) error rate of 0.05] * For example, if one subgroup had a percent change of 13%, the other subgroup would need a percent change of 36% to statistically conclude there is a difference.		

1239

1240 **9.2 Data Analysis**

1241 The analysis plans below are written with respect to the majority of outcomes of interest.

1242 Analyses will include data on both eyes for each participant, and confidence intervals will adjust  
1243 for correlation between two (2) eyes of the same participant.

1244 **9.2.1 Registry Data Analysis**

1245 The following Registry data analysis considerations focus on **Registry Objective 2** (see section  
1246 1.3). *Applicability of within-gene objectives will depend on within-gene sample size as noted  
1247 below. If less than 20, limit primary objective to describing the cohort in the form of case  
1248 histories. Objectives may still be explored depending on the needs for a specific gene.*

1249

1250 **Registry Objective 2 (Cross-Sectional Phenotype Characterization)**

1251 ➤ **Registry Objective 2** is to characterize cross-sectional retinal dystrophy associated with  
1252 disease-causing genetic variants using functional and structural measures (visual acuity,  
1253 OCT, static perimetry), **within-gene**. Structure-function relationships and risk factors for  
1254 disease severity will also be explored **within-gene**.

1255 ○ The distribution of each cross-sectional outcome measure will be summarized  
1256 (including tabulating categorically, as well as means, SDs, medians, quartiles,  
1257 ranges; *where sample size 20 or more*).

- 1258 ○ Scatterplots and Spearman correlation coefficients between cross-sectional  
 1259 outcome measures will be explored (*where sample size is 20 or more*)
- 1260 ○ Possible risk factors (genotype, phenotype, environmental, and comorbidities)  
 1261 for cross-sectional outcome measures will be explored (*where sample size is*  

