 1262 *40 or more*).
- 1263 ○ Methods will include univariate and multivariate analysis of  
 1264 covariance (ANCOVA) models. A stepwise selection procedure will  
 1265 be used to build the final model. A threshold of  $P < 0.10$  will be used to  
 1266 add to the model, and a threshold of  $P < 0.05$  will be used to remain in  
 1267 the multivariate model. Linearity of continuous factors will be  
 1268 assessed, and possibly quadratic or cubic terms will be considered if  
 1269 non-linear.
- 1270 ○ Potential risk factors to evaluate include:
- 1271     ▪ Phenotypic:
- 1272         • Clinical diagnosis (if applicable)
- 1273         • Duration of disease
- 1274         • Age of onset of initial vision symptoms
- 1275         • Gender
- 1276         • Race/ethnicity
- 1277         • Visual acuity
- 1278         • Lens Status (phakic/pseudophakic/aphakic)
- 1279     ▪ Genotypic:
- 1280         • Characterizations of the variants
- 1281     ▪ Environmental factors
- 1282         • Smoking status
- 1283         • Vitamin A use
- 1284         • Docosahexaenoic acid (DHA) use
- 1285         • Lutein use
- 1286 ○ Variability of symmetry of left and right eye cross-sectional outcome  
 1287 measures will be evaluated by scatterplots. Bland-Altman plots of the inter-  
 1288 eye difference versus the mean value will be inspected and a linear regression  
 1289 model for the differences will be used to test whether the intercept (overall  
 1290 mean difference) and slope is 0. The plot will be inspected to evaluate whether  
 1291 variability between eyes changes with greater mean values. The intraclass  
 1292 correlation coefficient of the values and the within-person variance will be  
 1293 estimated.

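### The Registry slope test for inter-eye symmetry (9.2.1) has no stated protection against scatter that changes with the mean; for EZ area the usual regression P value would reject true symmetry too often

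*Protocol*

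**What the plan says.** Section 9.2.1, last bullet under Registry Objective 2, sets out the symmetry analysis in one run of text: "eye difference versus the mean value will be inspected and a linear regression" "model for the differences will be used to test whether the intercept (overall" "mean difference) and slope is 0. The plot will be inspected to evaluate whether" "variability between eyes changes with greater mean values. The intraclass" correlation coefficient and the within-person variance are then estimated.

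The objective covers three measures within gene: acuity, OCT and static perimetry ("disease-causing genetic variants using functional and structural measures (visual acuity" and so on). Section 1.3 attaches the condition "Ideally where within-gene sample size is 20 or more" to the within-gene characterization.

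The bullet names no standard-error method, weighting, measurement scale or significance level. The protocol's "error rate of 0.05" appears in section 9.1.3, for Figure 9-1 and the NHS Objective 3 example, not here. The parallel NHS symmetry analysis (section 9.2.2, Other Planned Analyses) lists Bland-Altman plots and an intraclass correlation but no regression test.

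**The concern.** The question is whether right and left eyes differ systematically, and whether any difference drifts with the level of the measure. If the eyes are exchangeable, the true slope is 0. The usual regression t test is then correct only if the scatter of the differences does not grow with distance from the average mean. If it grows, the standard error of the slope is too small and the test rejects because asymmetry is larger in some people than in others, not because right differs from left.

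The bullet itself anticipates changing scatter but leaves it to visual inspection, with no effect on the test. EZ area is where this is hardest to avoid. It cannot be negative, so the absolute difference cannot exceed twice the mean and must shrink near zero, and the reference values put much of the distribution there. At stake is a descriptive statement, made gene by gene, that a right-left difference changes with disease extent when it does not.

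**Working it through.** **Inputs.** Reference mean (SD) from the Registry Sample Size Example in 9.1.2: EZ area 3.6 (5.6) mm², V_tot 27.8 (23.7) dB-sr, acuity 77.9 (11.7) letters. Inter-eye correlation r = 0.8 from 9.1.1 ("assume an inter-eye correlation of 0.8 throughout all sample size calculations throughout section"). N from 20 (section 1.3) to 100 (the within-gene cap). Two-sided 5% is assumed. The pattern of inter-eye scatter is not given and is also assumed, so a range is shown.

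**The plan's own figures.** None is stated for this test. As an input check, the half-widths in 9.1.2 reproduce: N = 50 gives an effective N of 100/1.8 ≈ 56, and t(0.975, 55) × SD/√56 is 1.34, 2.68 and 5.36 for SD 5, 10 and 20, against 1.3, 2.7 and 5.4 in the tables.

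**Why EZ scatter cannot be constant.** Let D = right − left and M = the pair mean. SD(D) = 5.6 × √(2 × 0.2) = 3.54 mm², about the mean itself, while |D| ≤ 2M. A skewed person value plus constant error does give 5% rejection, but with a gamma person value 24% of simulated eyes have negative area.

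**Large-sample size.** The variance of the slope that the usual test reports is too small by the factor k = E[(M−μ)²σ²(M)] / (Var(M) × E[σ²(M)]), where μ is the average of M and σ²(M) is the variance of D at M. The false-rejection rate tends to 2[1 − Φ(1.96/√k)]. Constant scatter gives k = 1 and 5%. If M is gamma with shape a and scatter is proportional to M, then k = (a+6)/a.
- EZ: SD(M) = 5.6√0.9 = 5.31; a = (3.6/5.31)² = 0.459; k = 14.1; √k = 3.75; rate about 60%.
- V_tot: SD(M) = 23.7√0.9 = 22.5; a = (27.8/22.5)² = 1.53; k = 4.92; √k = 2.22; rate about 38%.

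These are limits. Simulation with proportional error at N = 20 to 100 gave 49–55% and 29–35%.

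**Simulated false rejection of slope = 0, exchangeable eyes, r about 0.8, N = 20 to 100:**

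| Measure | Assumed shape | Rejection |
|---|---|---|
| Any | bivariate normal, constant scatter | 5% |
| EZ area | lognormal | 50–64% |
| EZ area | gamma margins, Gaussian copula | 40–45% |
| EZ area | shared-gamma | 21–30% |
| EZ area | bounded beta (assumed ceiling) | 20–25% |
| EZ area | constant error clipped at zero | about 8% |
| V_tot | lognormal | 34–46% |
| V_tot | gamma | 20–25% |
| V_tot | bounded beta, or clipped constant error | about 4–6% |
| Acuity | ceiling minus lognormal | 24–33% |
| Acuity | ceiling minus gamma | 14–20% |
| Acuity | bounded beta on 0–97 | about 7.5% |

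For gamma margins the results barely move at r = 0.5 or 0.9 (EZ 42–45% and 39–44%).

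**Alternatives.** HC3 robust standard errors, N = 20 to 100, gamma shapes: EZ 13.6% falling to 8.7%, V_tot 10.4% to 7.1%, acuity 8.7% to 6.4%. Swapping eye labels within person held about 3–7% across the runs made. A paired t test of the mean difference gave 1.7–5.8%.

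**The case against.** The text does not say ordinary least squares. A robust or weighted fit, or a transformed scale, is compatible with its wording and could be fixed in a statistical analysis plan that is not shown. The protocol also looks for changing variability in the very next sentence. Both points stand as far as they go. They do not dispose of the matter: an unqualified linear regression test is normally read as the usual t test, the inspection has no stated consequence, and the obvious robust alternative (HC3) still leaves about 9–14% for EZ area with gamma margins.

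A reader might infer more than the document supports:
- That the test is badly wrong for all three measures. The protocol gives no inter-eye scatter pattern. Scatter that shrinks at both floor and ceiling can bring V_tot back to about 5% and acuity to about 7.5%.
- That any non-constant variance inflates the error. It does so only when scatter rises with squared distance from the average mean.
- That the error always worsens with N. Some acuity runs were flat (14.9%, 17.9%, 17.7% at N = 20, 50, 100) and the bounded shapes do not rise. The supportable statement is that the excess does not disappear.
- That many genes would be misreported. With 1,500 participants at most 1,500/20 = 75 genes can reach N = 20 and 1,500/50 = 30 can reach N = 50, and no P-value-driven reporting rule is stated.

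**Conclusion.** The point holds for EZ area. With exchangeable eyes, the usual slope test at an assumed two-sided 5% rejects about 20–64% of the time under the gamma, lognormal and bounded shapes tried, and about 8% in the mildest case run. The mechanism follows from non-negativity and an SD above the mean. The exact size rests on assumed shapes, including an assumed ceiling for the bounded one. For V_tot and acuity the rate is uncertain (about 4–46% and 7.5–33%), and for V_tot there may be no excess.

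Importance is low. This is one descriptive sub-analysis; no eligibility rule, sample size, NHS gene selection or main inference depends on it. It is an optional improvement (a COULD), worth making because it is cheap.

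**What to change.** In 9.2.1, keep the regression slope as the statistic but obtain its P value by randomly swapping right/left labels within participant, that is, flipping the sign of D with M unchanged. Under exchangeable eyes this reproduces the null whatever the variance pattern. Test the overall mean difference with a paired test of the differences; the intercept of an uncentred fit is the fitted difference at an inter-eye mean of zero, not the overall mean difference. Keep the Bland-Altman plots, the inspection, the intraclass correlation and the within-person variance. A rank correlation of |D| with M is an optional addition that would put a test behind the inspection.

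The cost is a sentence or two of wording and a few lines of code, with no new data. There will be fewer slope flags and lower apparent power. In one run (right eyes 30% larger, N = 50, EZ gamma margins) the usual slope test rejected 72%, but it rejects 43% with no difference at all; the swap slope test rejected 26% and a swap test of the mean difference 49%. The swap P value is exact for exchangeable eyes, so it should be read alongside the paired test when a constant right-left shift is present.

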### 1294 9.2.2 Natural History Data Analysis

1295 The following Natural History Study data analysis considerations focus on **NHS Objectives 1-3**  
 1296 (see section 1.3). *Applicability of within-gene objectives will depend on within-gene sample size*

1297 *as noted below. **If less than 20, limit primary objective to describing the cohort in the form of***  
 1298 ***case histories. Objectives may still be explored depending on the needs for a specific gene.***  
 1299

1300 **NHS Objective 1 (Natural History)**

- 1301 ➤ **NHS Objective 1** is to characterize the natural history of retinal degeneration associated  
 1302 with disease-causing genetic variants over 4 years, using functional, structural, and  
 1303 patient-reported outcome measure, **within-gene** (*where sample size 20 or more*).
- 1304 ○ **Analysis plan for functional and structural measures:** The distribution of each  
 1305 outcome at each visit will be summarized (including tabulating categorically, as  
 1306 well as means, SDs, medians, quartiles, ranges; both the absolute change and  
 1307 percent change will be evaluated, tests performed multiple times will be analyzed  
 1308 using average of all available tests). To determine the average annual rate of  
 1309 progression in the population for each outcome, a repeated measure least squares  
 1310 regression model will be fit using all available outcome data at baseline and all  
 1311 annual visits. Multiple imputation will be used to impute the outcome values for  
 1312 all missing time points (including participants who discontinue follow up prior to  
 1313 48 months). Secondary analyses using binary definitions of outcome measures  
 1314 will also be explored in time to event analyses; Kaplan-Meier estimates with 95%  
 1315 confidence intervals will be calculated.
- 1316 ○ **Analysis plan for PRO measures:** The scoring of each questionnaire will be  
 1317 completed according to the procedures for each instrument and is detailed further  
 1318 in a separate statistical analysis plan. Baseline scores will be cross tabulated with  
 1319 categorical (severity of disease) versions of the outcome measures of interest at  
 1320 baseline. Changes in scores will be cross tabulated with binary (progression of  
 1321 disease) versions of the outcome measures of interest at the 24- and 48-month  
 1322 visits. A generalized linear model adjusted for baseline differences will be  
 1323 explored.

1324 **NHS Objective 2 (Structure-Function Relationship)**

- 1325 ➤ **NHS Objective 2** is to explore whether structural outcome measures can be validated as  
 1326 surrogates for functional outcomes in individuals with disease-causing genetic variants,  
 1327 **within gene** (*where sample size 20 or more*).
- 1328 ○ **Analysis plan:** Scatterplots and Spearman correlation coefficients of changes in  
 1329 functional and structural outcome measures of progression from baseline to each  
 1330 visit will be evaluated.

1331 **NHS Objective 3 (Risk Factors for Progression)**

- 1332 ➤ **NHS Objective 3** is to explore possible risk factors (genotype, phenotype,  
 1333 environmental, and comorbidities) for progression of the outcome measures at 4 years in  
 1334 individuals with disease-causing genetic variants, **within-gene** (*where sample size 40 or*  
 1335 *more*).
- 1336 ○ **Analysis plan:** The distribution of each outcome in terms of both absolute  
 1337 change and percent change from baseline to 4 years will be summarized  
 1338 (including tabulating categorically, as well as means, standard deviations,

1339 medians, quartiles), stratified by categorical levels of each potential risk factor  
 1340 of interest (listed below). Potential risk factors to evaluate include:

- 1341 ○ Phenotypic:
  - 1342 ■ Clinical diagnosis (if applicable)
  - 1343 ■ Duration of disease
  - 1344 ■ Age of onset of initial vision symptoms
  - 1345 ■ Gender
  - 1346 ■ Race/ethnicity
  - 1347 ■ Visual Acuity
  - 1348 ■ Lens Status (phakic/pseudophakic/aphakic)
- 1349 ○ Genotypic:
  - 1350 ■ Characterizations of the variants
- 1351 ○ Environmental factors
  - 1352 ■ Smoking status at baseline
  - 1353 ■ Vitamin A use at baseline
  - 1354 ■ Docosahexaenoic acid (DHA) use at baseline
  - 1355 ■ Lutein use at baseline

1356 **Other Planned Analyses**

- 1357 ➤ Analysis plan for variability of repeat perimetry testing at baseline: Scatterplots and  
 1358 Spearman correlation coefficients for pairs (first versus second) of testing values for each  
 1359 repeated perimetry test. Bland-Altman plots of difference versus the mean value will be  
 1360 inspected. The intraclass correlation coefficient of the values and the within-eye variance will  
 1361 be estimated.
- 1362 ➤ Analysis plan for the symmetry of left eye versus right eye: At baseline and each subsequent  
 1363 testing time, the symmetry of the test result values from the left and right eyes will be  
 1364 assessed and the symmetry of the change from baseline from the left and right eyes will be  
 1365 assessed for each follow-up visit. Bland-Altman plots of the inter-eye difference versus the  
 1366 mean value will be inspected. The intraclass correlation coefficient of the values will be  
 1367 estimated.

1368 **2.3 Interim Data Analysis**

1369 No formal interim analysis or “stopping guidelines” are planned for determining early stopping  
 1370 according to statistical rules, as no intervention is being studied and thus early efficacy and  
 1371 safety signals are not applicable.

1372 Interim analyses will be planned for other reasons, including to evaluate data at baseline and  
 1373 annual visits for reporting in preliminary manuscripts, as well as monitoring data for recruitment  
 1374 and retention benchmarks, and quality assurance throughout the duration of the study. The FFB  
 1375 Consortium Executive Committee will review and oversee these data and their use in reporting.

1376

1377

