	Key Assessments	Test	Equipment	Reading Center	Registry (R) or Natural History Study (NHS)
	Visual field sensitivity measured with quantitative topographic analysis (hill of vision [HOV])	Static Perimetry (SP)	Octopus 900 Pro	Yes	R, NHS
	Early Treatment of Diabetic Retinopathy Study (ETDRS) / HOTV Best Corrected Visual Acuity (BCVA) letter score	Visual Acuity (VA)	Electronic Visual Acuity (EVA) system or ETDRS/HOTV charts	N/A	R, NHS
	Low visual acuity test – for participants unable to see ETDRS letters	Low Visual Acuity	Berkeley Rudimentary Vision Test (BRVT)	N/A	R, NHS
	ETDRS/HOTV best corrected low luminance visual acuity letter score	Low Luminance Visual Acuity (LLVA)	Electronic Visual Acuity (EVA) system or ETDRS/HOTV charts	N/A	R, NHS
	Mean retinal sensitivity	Fundus guided Microperimetry (MP)	MAIA	Yes	NHS
	Contrast sensitivity function	Contrast sensitivity	CSV-1000E chart	N/A	NHS
	Retinal function using amplitudes and timing in response to rod- and cone-specific stimuli	Full-field Electroretinogram (ffERG)	Diagnosys Espion	No	NHS
	Full-field retinal sensitivity	Full-field stimulus threshold (FST) testing to blue, white, and red stimuli	Diagnosys Espion	No	NHS
Color vision function	Color vision	Lanthony D15	N/A	NHS	
Structural Outcomes:					
Key Assessments	Test	Equipment	Reading Center	Registry (R) or Natural History Study (NHS)	
Ellipsoid zone (EZ) area; outer nuclear layer and ganglion cell layer thicknesses	Spectral Domain Optical Coherence Tomography (SD-OCT)	Heidelberg Spectralis	Yes	R, NHS	

	
Qualitative and quantitative assessments of autofluorescence pattern
	
Fundus Autofluorescence (FAF)
	
Optos
	
Yes
	
NHS

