Vision Cohort 2 Approximately 450 participants	Criteria that must be met in the better eye* at the Registry/Screening Visit: ○ visual acuity ETDRS letter score of 19-53 (approximate Snellen equivalent 20/100 to 20/400) OR

	○ visual acuity ETDRS letter score of 54 or more (approximate Snellen equivalent 20/80 or better) and visual field** diameter less than 10 degrees in any meridian of the central field
Vision Cohort 3 Approximately 150 participants	Criteria that must be met in the better eye* at the Registry/Screening Visit: ○ visual acuity ETDRS letter score of 18 or less (approximate Snellen equivalent 20/500 or worse)
*Better Eye	The better eye is defined as the eye with the better Registry/Screening Visit ETDRS visual acuity. However, if both eyes have the same visual acuity, which is defined as the same Snellen equivalent, then the determination will be made at the Investigator’s discretion. In this scenario, the Investigator will consider the eye with better fixation or clearer ocular media to permit highest quality retinal imaging.
**Visual Field	The visual field (VF) is defined as the clinically determined kinetic VF III4e performed within the last 18 months prior to the Registry/Screening Visit or performed on the day of the Registry/Screening Visit.

237

238 **Vision Cohort Grid**

	VF diameter <math>\geq 10^\circ</math> in every meridian	VF diameter <math>< 10^\circ</math> in any meridian
20/80 or better	Vision Cohort 1	Vision Cohort 2
20/100-20/400	Vision Cohort 2	Vision Cohort 2
20/500 or worse	Vision Cohort 3	Vision Cohort 3

239

240 **Younger Age Cohort Definition**

Younger Age Cohort	
 
• Participants who are between the ages of <math>\geq 4</math> years and <math>< 8</math> years old will be designated as the Younger Age Cohort.
 
• Participants in this cohort will not be assigned a Vision Cohort.
 
• Registry/Screening Visit and Natural History Study Visits will have an abbreviated testing schedule.
 

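### Percent change is a poor scale for letter scores and other outcomes whose Baseline can be near zero, and the example's acuity precision applies only to eyes near 78 letters

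*Protocol*

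**What the plan says.** - **Analysis.** Section 9.2.2, Objective 1, plans summaries of absolute change and then percent change for every functional and structural outcome ("percent change will be evaluated, tests performed multiple times will be analyzed"). Objective 3 plans both scales again for change from Baseline to 4 years, split by levels of each risk factor. Visual acuity is one of the listed factors. Neither objective limits percent change by measure or by Baseline level.
- **Sample size.** Section 9.1.3 adopts percent change for all measures, for simplicity. Section 4.1 says that within-gene sample sizes can be justified from chapter 9.
- **Worked example.** For a gene with 50 participants, the acuity SD is set at 5%. The source line reads "Visual Acuity: -2.3 (5.1", that is, a mean of -2.3% and an SD of 5.1% at 24 months. The source cohort's Baseline acuity averaged 77.9 letters (SD 11.7). The example gives half-widths of 1%, 5% and 8% for acuity, EZ area and static perimetry. It says that two groups of 25 "would have about 80% power to conclude there is a difference if the true difference is" 4%, 15% and 23% respectively.
- **Who is included.** Vision Cohort 3 is defined in section 2.2 by a better-eye "ETDRS letter score of 18 or less (approximate Snellen equivalent 20/500 or worse". The Outcomes table provides a low-vision test "for participants unable to see ETDRS letters". Section 9.2 analyses both eyes, although the cohort is set by the better eye.

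**The concern.** A percent change divides by the Baseline value. When that value is small, a few letters of ordinary test variation become a large percentage. When it is zero, the percentage does not exist. In a gene that mixes Vision Cohorts, the mean and SD of percent change in acuity can then mainly describe the few worst eyes.

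Objective 3 is the most exposed. Splitting percent change by Baseline acuity means dividing the outcome by the stratifying variable. Any factor correlated with Baseline acuity would inherit the same artefact; duration of disease is a plausible one. A future trial could take such a gradient for faster progression.

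The precision quoted for acuity is also at stake. It is borrowed from a high-acuity cohort, while the framework is meant to serve any gene in the study.

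**Working it through.** **1. The plan's own figures.** Inputs from sections 9.1.1 and 9.1.3: N=50; "Inter-eye correlation = 0.8"; Type I "error rate of 0.05" (two-sided assumed, as the sidedness is not stated).

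- Effective N = 50 × 2/(1+0.8) = 55.6, shown as 56 in the tables.
- Half-width = t(0.975; 55) × SD/√56 = 0.2678 × SD. SDs of 5%, 20% and 30% give 1.34%, 5.36% and 8.03%, against the stated 1%, 5% and 8%. All of Table 9-5 reproduces after rounding.
- Detectable difference by a two-sample t test at 80% power, with 25 × 1.11 = 27.8 effective per group: 3.8%, 15.3% and 23.0%, against 4%, 15% and 23%. In SD units this is 3.83/5 = 0.766.

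The example is arithmetically right for the SDs it assumes.

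**2. The same loss at different Baselines.** 4/78 = 5%; 4/36 = 11%; 4/18 = 22%. Eyes losing identical letters show a more than fourfold gradient across acuity levels.

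**3. What the 5.1% implies in letters.** 0.051 × 77.9 = 3.97 letters. This conversion is approximate, because a percent SD times a mean Baseline does not exactly recover the SD in letters. If 3.97 letters is assumed at every level, the SD of percent change is 3.97/Baseline:

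| Baseline letters | 77.9 | 54 | 36 | 18 | 9 | 5 | 0 |
|---|---|---|---|---|---|---|---|
| SD of percent change | 5.1% | 7.4% | 11% | 22% | 44% | 79% | undefined |

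**4. A mixed gene at N=50.** Assume the Registry-wide targets of 900:450:150 hold within the gene (60:30:10), and ignore differences in mean percent change between cohorts.

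- Typical scores 78, 54 and 18: SD = √(0.6×5.1² + 0.3×7.4² + 0.1×22.1²) = 9.0%. Half-width = 0.2678 × 9.0 = 2.4%.
- Typical scores 78, 36 and 9: SD = √(0.6×5.1² + 0.3×11.0² + 0.1×44.1²) = 15.7%. Half-width = 4.2%. Cohort 3 supplies 0.1×44.1²/15.7² = 79% of the variance.

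A simulation spread Baselines uniformly within each cohort (54–90, 19–54, and up to 19 letters). It gave 2.3% for Cohorts 1 and 2 alone at 2:1. With 10% Cohort 3 it gave 3.4%, 4.1% and 5.8% when the lowest Baseline was 10, 5 and 1 letters.

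**5. The same example in letters.** Half-width 0.2678 × 3.97 = 1.06 letters; detectable difference 0.766 × 3.97 = 3.0 letters. Under the constant-SD assumption neither depends on the cohort mix.

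**6. Other measures.** SD divided by mean at Baseline in the source cohort: acuity 11.7/77.9 = 0.15; V_tot 23.7/27.8 = 0.85; EZ area 5.6/3.6 = 1.56. For an area, which cannot be negative, an SD above the mean makes many near-zero values likely. The protocol's microperimetry repeat rule (section 4.3.2) supplements its 50% relative limit with an absolute 0.5 dB limit, which fits ratios being unstable near zero. The percent-change analysis has no such companion rule.

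**The case against.** The strongest reply is that most of the remedy is already planned. Absolute change stands beside percent change in both objectives, and medians and quartiles would expose a few extreme percentages. The annual-rate regression names no percent scale, patient-reported outcomes use score changes, and Objective 2 uses rank correlations. Section 9.2 says the plans are written for the majority of outcomes, which leaves room for exceptions. The example is a template, and Table 9-5 covers SDs from 5% to 60%: at N=50 it gives 3% for an SD of 10% and 5% for 20%, which brackets the results above. All of this is correct. It narrows the point but does not remove it, because the two scales have equal standing in 9.2.2, percent is the only scale in 9.1.3, and nothing tells a user when to leave the 5% row.

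Some stronger readings are tempting but not supported:

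- **That low-vision eyes drive the 1% acuity precision.** They do not. It follows from an SD of 5%, taken from a cohort averaging 77.9 letters. The difficulty is that low-vision eyes are scarcely represented in it.
- **That Cohort 3 distorts every functional measure.** Its Natural History Study schedule has no static perimetry, microperimetry or contrast sensitivity. For those measures, near-zero Baselines would have to come from other participants.
- **That letter and dB scales have an arbitrary zero, so percentages are meaningless.** The protocol does not say so, and the point does not need it. The objection that V_tot, in dB-sr, should then be treated like microperimetry has some force; keeping it on a percent scale is a judgement that relies on the Baseline minimum.
- **That the absence of a zero-Baseline rule is an omission.** Such a rule may sit in the separate statistical analysis plan.

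**Conclusion.** The point holds as a matter of scale. For letter scores, and for other outcomes whose Baseline can be at or near zero, mean percent change is undefined or dominated by low-Baseline eyes. In Objective 3 it is mathematically tied to a listed risk factor. That rests on arithmetic and the study's own eligibility, with no further assumption.

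The example's 1% and 4% are correct for an SD of 5% but may be optimistic for a gene with Cohort 2 or 3 eyes. The range of roughly 2.4% to 4.2% is illustrative. It rests on a constant SD of about 4 letters, chosen typical scores, a 24-month SD carried to 4 years as the protocol itself does, and a Registry-wide mix applied to one gene. The protocol states no within-gene share for Cohort 3. The range should not be read as a corrected value, and no table is wrong.

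**What to change.** - **Section 9.2.2, Objectives 1 and 3:** make absolute change the scale for inference and risk-factor comparison for visual acuity, low luminance acuity, microperimetry, FST and contrast sensitivity. Report percent change only for EZ area and V_tot, in eyes above a pre-stated measurable Baseline minimum, and give the number of eyes below it.
- **Section 9.1.3 example:** state acuity in letters, with an SD of about 4.0 as a declared assumption, a half-width of about 1.1 letters and a detectable difference of about 3 letters. Alternatively, keep the 1% and 4%, say that they apply only to genes with Baseline acuity near 78 letters, and direct other genes to a larger-SD row of Table 9-5.

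The cost is wording in two sections. Absolute change is already planned, so no data collection or analysis is added. The downside is that the measures no longer share one percent scale, which makes comparison across outcomes less direct.
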